Pioglitazone for Idiopathic Gastroparesis NCT04300127 8/24/2020

Clinical Protocol Synopsis- Pioglitazone for the Treatment of Gastroparesis

Title

Pioglitazone for the Treatment of Idiopathic Gastroparesis (PIOGAS Study)

Type of study

• Open label pilot study

Objective

- The principal objective of this pilot study will be to evaluate whether 8 weeks of treatment of pioglitazone will improve symptoms as measured by the Gastrointestinal Symptom Index Daily Diary (GCSI-DD) in patients with Idiopathic Gastroparesis
- Secondary objectives of this study include:
 - To determine the effects of pioglitazone on other symptoms associated with gastroparesis using the Patient Assessment of Upper Gastrointestinal Symptom Severity Index (PAGI-SYM) and the Gastrointestinal Symptom Rating Scale (GSRS),
 - To determine the effects of pioglitazone on gastric emptying as measured by the ¹³C- Spirulina breath test,
 - To determine the effects of pioglitazone on satiety as measured by a liquid caloric test
 - To determine the effects of pioglitazone on depression and anxiety using the Beck Depression Inventory and State-Trait Anxiety Scores,
 - To determine the effects of pioglitazone on Quality of Life using the PAGI-QoL and SF-36 questionnaire,
 - To determine the effects of pioglitazone on markers of inflammation (CRP and ESR) and serum cytokine levels
 - And to determine the nature and incidence of adverse effects from a 12-week course of pioglitazone.

Treatment group

• Pioglitazone (30 mg po qd)

Population

 Age 18 years or older at registration with nausea, vomiting, and other symptoms suggestive of patients with chronic nausea and vomiting of presumed gastric origin, with symptomatic gastroparesis.

Study duration

- Up to 4 weeks of screening prior to pioglitazone treatment
- 8 weeks of treatment starting at initial dose of pioglitazone
- **4 weeks** of washout period
- Length of recruitment: 16 months

Sample size justification

- Total of **20 patients**
- Primary comparison: Baseline PAGI-SYM score versus 4, 8, and 12 weeks.

Number of clinical centers

- Johns Hopkins Bayview Medical Center.
- Mayo Clinic Scottsdale, Arizona This site will not perform enrollment of patients, It will only intervene as data analysis center under the supervision of [name].
- •

Inclusion criteria

- Age 18 years or older at registration

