- (3) Inflammatory Markers
 - CRP and ESR
- (4) Mood and Behavior
 - Beck Depression Inventory
 - State-Trait Anxiety
- (5) Adverse Events
 - Biochemical tests
 - Symptoms of cardiac or pulmonary disease
 - Any other AE reported or noted throughout the study and follow-up

Justification of sample size

This will be a pilot study recruiting 20 candidates.

Statistical analysis

All analyses will be on an intention-to-treat basis. Patients who do not have any of the decline of 1 or more in the total GCSI score recorded during the period of treatment will be counted as not improved (i.e., 0) for the primary outcome. Comparisons will also be made with baseline total GCSI score and other secondary outcomes. Numerical changes will be analyzed by descriptively comparing the between-treatment group differences in mean and median changes; P-values will be derived from Wilcoxon rank sum tests for comparison of the distribution of changes in each group The two-sided P-values so derived will be reported in the primary results paper of the trial. A two-sided P-value of 0.05 will be considered statistically significant.

Standard treatment recommendations

During the screening period, patients will receive a standardized set of recommendations to include dietary modification. The patient's medications are reviewed to eliminate drugs that might exacerbate the underlying dysmotility disorder or prevent the beneficial actions of a prokinetic agent. Dietary modification and use of pain medications as appropriate are the primary management approaches. If symptoms require further treatment during the trial, patients will be instructed to take rescue medications that they would usually take such as prochlorperazine for nausea and vomiting, and tramadol for abdominal pain. These recommendations have been prepared by the GpCRC Steering Committee as standard of care in the management of patients with gastroparesis or related disorders. This will help ensure that the patients in both treatment groups receive standard of care treatment.

Visit schedule

- Screening: at least 1 visit separated by at least 1 calendar day prior pioglitazone treatment; screening period can last no more than 4 weeks after registration
- Final pre-treatment interview, dispensing of study agent
- Follow-up visits: every 4 weeks after pioglitazone treatment throughout the 12 week study
- Post-treatment: follow-up at **16 weeks**

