- Gastrointestinal Symptom Rating Scale (GSRS)
- Health-related quality of life questionnaire (SF-36v2)
- Beck Depression Inventory (BDI-II)
- State Trait Anxiety Inventory (STAI)
- NIH Patient Reported Outcome Measurement Information System (PROMIS) gastrointestinal symptom scales.

Anthropomorphic assessments (body weight, body height, body mass index [BMI], waist circumference, hip circumference, vital signs (systolic and diastolic blood pressure, heart rate, respiratory rate, body temperature); and general physical findings will be collected. Laboratory test results that need to be recorded from chart review or obtained as part of screening include: CBC (complete blood count), metabolic panel (sodium, potassium, chloride, bicarbonate, calcium, BUN, creatinine, alanine aminotransferase (ALT), aspartate aminotransferase (AST), magnesium, albumin, total protein). Glucose and hemoglobin A1c will be measured in patients with diabetes.

(2) Treatment Start Visit

At this visit the patient is issued the study medication. Treatment can only start after eligibility has been fully checked and all data collected at screening visits have been keyed to the trial database. Women of childbearing potential must have a negative pregnancy test. Medication can be delivered to patient home address from the Bayview IDS pharmacy

The GCSI-DD completed by the patient each night for one week will be collected by the clinical center staff. After initial dose of pioglitazone, the patients will be provided thee week supplies of the GCSI-DD for completion each night before bed.

After eligibility is confirmed with the PIOGAS web-based data management system, treatment can begin. The date of starting treatment is the start (zero) time for reckoning follow-up visits.

(3) Follow-up visits

Patients will return for follow-up visits at 4, 8 and 12 weeks after treatment has begun. The specific procedures to be completed at each of the follow-up visits are:

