Week 4 visit: Medical history including clinical global patient impression (GCPI) questionnaire. The following questionnaires should be completed: Patient Assessment of Upper Gastrointestinal Disorders Symptom Severity (PAGI-SYM), NIH Patient Reported Outcome Measurement Information System (PROMIS) gastrointestinal symptom scales. Review study drug adherence and tolerance of the study drug with the participant. The daily GCSI-DD completed by the patient each night since beginning treatment will be collected by the clinical center staff.

In addition the patient will be provided 4 weeks of GCSI-DD for completion each night before bed.

- Week 8 visit: Medical history including clinical global patient impression (GCPI) • questionnaire. The following questionnaires should be completed: Patient Assessment of Upper Gastrointestinal Disorders Symptom Severity (PAGI-SYM), NIH Patient Reported Outcome Measurement Information System (PROMIS) gastrointestinal symptom scales. Review study drug adherence and tolerance of the study drug with the participant. The GCSI-DD completed by the patient each night since the last visit will be collected by the clinical center staff. In addition the patient will be provided 4 weeks GCSI-DD for completion each night before bed. Laboratory test results that need to be recorded from chart review or obtained as part of screening include: CBC (complete blood count), metabolic panel (sodium, potassium, chloride, bicarbonate, calcium, BUN, creatinine, alanine aminotransferase (ALT), aspartate aminotransferase (AST), magnesium, albumin, total protein). CRP and ESR
- Week 12 visit: Medical history, physical exam including clinical global patient impression (GCPI) questionnaire. The following questionnaires should be completed: Patient Assessment of Upper Gastrointestinal Disorders Symptom Severity (PAGI-SYM), Gastrointestinal Symptom Rating Scale (GSRS), Health Survey (SF-36v2), Beck Depression Inventory (BDI-II), and State Trait Anxiety Inventory (STAI), NIH Patient Reported Outcome Measurement Information System (PROMIS) gastrointestinal symptom scales. Review study drug adherence and tolerance of the study drug with the participant. The GCSI-DD completed by each the patient night since the last visit.

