Anthropomorphic assessments (body weight, body height, body mass index [BMI], waist circumference, hip circumference, vital signs (systolic and diastolic blood pressure, heart rate, respiratory rate, body temperature); and general physical findings will be collected.

• Week 16 visit: This will be a terminal visit. Medical history including side effect or symptom profile, and include a questionnaire for global overall relief of symptoms question and clinical global patient impression question.

PIOGAS Study Data Collection Schedule								
	Screening & Pioglitazone treatment Visits		Follow-up Visits: Weeks from start of treatment					
	Screening	Treatment initiation	4	8	12			
Consent	Х							
Gastric emptying scintigraphy results review	Х							
Baseline medical history	Х							
GCSI-DD	Х		Х					

			N N		
Collection of GCSI-DD			Х	Х	Х
PAGI-SYM questionnaire	Х		Х	Х	Х
GSRS questionnaire	X				Х
SR-36v2 Healthy Survey questionnaire	Х				Х
Beck Depression Inventory-II	Х				Х
State Trait Anxiety Inventory	X				Х
PROMIS NIH scale	Х		Х	Х	Х
Physical exam	Х				Х
Study drug dispensed		Х			
Follow-up medical history, including			Х	Х	Х
review of adverse events					
CBC, CMP	Х			Х	
HbA1c	X				
CRP & ESR	Х			Х	
12-lead EKG	Х				
Pregnancy test	X				

Physical exam includes weight, vital signs (temperature, heart rate, blood pressure) and general physical findings **Complete blood count (CBC)**: white blood cells, red blood cells, hemoglobin, hematocrit, platelets **Complete metabolic panel (CMP)**: sodium, potassium, chloride, carbon dioxide, glucose, calcium, BUN, creatinine, bilirubin, ALT, AST, alkaline phosphatase, magnesium, albumin, total protein

Specific Tests and Questionnaires

- Laboratory Tests: All laboratory test results may be obtained as archival material from the patient's chart or should be collected as part of standard of care during screening. The etiologic tests required once as part of screening include: high-sensitivity C-reactive protein (hs-CRP); sedimentation rate (ESR); complete blood count (white blood cell count (WBC), red blood cell count (RBC), hemoglobin, hematocrit, platelet count); comprehensive metabolic panel (sodium, potassium, chloride, carbon dioxide, calcium, BUN, creatinine, glucose, and liver panel including total protein, albumin, total bilirubin, aspartate aminotransferase, alanine aminotransferase, alkaline phosphatase); and hemoglobin A1c.

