The adverse events reported in placebo-controlled clinical trials of pioglitazone are upper respiratory tract infections, headache, sinusitis, myalgia, tooth disorders, Diabetes Mellitus aggravated, pharyngitis, chest pain, decreased urine output, dilated neck veins, extreme fatigue, irregular breathing, irregular heartbeat, swelling of the face, fingers, feet, or lower legs, tightness in the chest, trouble breathing, weight gain, decreased hemoglobin and hematocrit, elevated liver function enzymes and creatine phosphokinase (CPK).

Adverse events will be evaluated in every follow up visit. A form of Adverse Event will be completed if the candidate complains of any symptom, sign, abnormal assessment or any combination of these. An adverse event can be an expected side effect that is of a serious nature, or an unexpected side effect/event regardless of severity.

This study will monitor and report adverse events to ensure patient safety to IRB and FDA. Signs and symptoms associated with the adverse event will be graded as to severity by the clinical site staff as mild, moderate, or severe using Version 4.03 of the National Cancer Institute's Common Terminology Criteria for Adverse Events (CTCAE).

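### CPK is a named laboratory risk but is never scheduled, and the lists and timing of the single post-baseline safety sample need reconciling

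*Combined protocol and SAP*

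**What the plan says.** The Risks section, drawing on earlier placebo-controlled trials, ends its list of reported effects with "decreased hemoglobin and hematocrit, elevated liver function enzymes and creatine phosphokinase (CPK"). The last secondary objective is to describe "adverse effects from a 12-week course of pioglitazone", and Outcome measures, item (5), includes "Biochemical tests".

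Blood tests are described in four places: the screening text under (1), the week 8 entry under (3) Follow-up visits, the PIOGAS Study Data Collection Schedule with its footnotes, and the Laboratory Tests item under Specific Tests and Questionnaires. The schedule ticks CBC and CMP at screening and at week 8. Its footnote defines CMP as "sodium, potassium, chloride, carbon dioxide, glucose, calcium, BUN, creatinine, bilirubin, ALT, AST, alkaline phosphatase, magnesium, albumin, total protein".

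The screening and week 8 texts open their lists with the same sentence: "Laboratory test results that need to be recorded from chart review or obtained as part of screening include: CBC (complete blood count), metabolic panel".

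On duration, the primary objective asks "whether 8 weeks of treatment of pioglitazone will improve symptoms", and Study duration gives 8 weeks of treatment followed by 4 weeks of washout. The safety objective quoted above refers to 12 weeks of drug.

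**The concern.** A safety outcome built on blood tests can report only on what is drawn, and when. The protocol itself names raised CPK as an effect of the drug, but plans neither a baseline nor an on-study value. The final report could then say nothing about its frequency, and a reader might take that silence as reassurance.

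The other named laboratory effects rest on one post-baseline sample per patient. For that sample to be interpretable, three things must be clear: which analytes it contains, that it was taken on study, and where it falls relative to dosing. The text leaves each of these open to more than one reading.

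**Working it through.** No power or precision figure is involved. The check is a comparison of the laboratory lists and the visit calendar.

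**Step 1: analytes.** Bicarbonate and carbon dioxide are counted as the same item.

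| Source | Chemistry analytes | Bilirubin | Alkaline phosphatase | Glucose | Magnesium | CPK |
|---|---|---|---|---|---|---|
| Screening text | 12 | no | no | only for patients with diabetes | yes | no |
| Week 8 text | 12 | no | no | no | yes | no |
| Schedule footnote (CMP) | 15 | yes | yes | yes | yes | no |
| Laboratory Tests item | 14 | yes | yes | yes | no | no |

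The footnote has 15 − 12 = 3 analytes that the week 8 text lacks: bilirubin, alkaline phosphatase and glucose. The first two matter most here, because raised liver enzymes are a named risk and the Laboratory Tests item counts both as part of the liver panel. ALT and AST are on every list. Hemoglobin and hematocrit are covered by the CBC. CPK is on none of the four lists, so planned CPK measurements are 0 per patient, and 20 × 0 = 0 in the trial.

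**Step 2: visits with safety bloods.** Patients attend as follows: "Patients will return for follow-up visits at 4, 8 and 12 weeks after treatment has begun". A terminal visit follows at week 16.

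- Week 4: the entry begins "Week 4 visit: Medical history including clinical global patient impression (GCPI) questionnaire" and continues with questionnaires, adherence, tolerance and diaries. No bloods.
- Week 8: CBC and metabolic panel, with CRP and ESR.
- Week 12: history, physical examination, questionnaires, adherence. No bloods.
- Week 16: history and global questions. No bloods.

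So 1 of 4 post-baseline visits has safety bloods. Visit text and schedule agree on this.

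**Step 3: is the week 8 sample new?** The schedule ticks it. The week 8 text, however, reuses the screening sentence, which allows chart results or results obtained at screening. The Laboratory Tests item also lets all results come from the chart. Read literally, a site could enter an existing result at week 8.

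**Step 4: position relative to dosing.**

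- If treatment is 8 weeks, week 8 is the end of dosing, and washout runs to week 8 + 4 = 12 with no bloods.
- If treatment is 12 weeks, week 8 falls during dosing, 12 − 8 = 4 weeks of dosing follow without bloods, and there is no end-of-treatment sample.

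The text gives support to both. Study duration and the primary objective say 8 weeks. The safety objective says 12, and study drug adherence is still reviewed at week 12.

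**The case against.** The strongest reply has four parts.

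- **The Risks list is not a promise to measure.** It recites events from other trials, including worsening of diabetes, although diabetes is an exclusion here, and the biochemical outcome names no analyte. This is fair as far as it goes. But the protocol makes adverse effects an objective and gives no reason for leaving CPK out, so the mismatch should be closed or explained.
- **A raised CPK could still be recorded.** An investigator might order one, for example for myalgia, and the adverse event form covers any abnormal assessment. This stands. A reader might infer that CPK elevation cannot be detected, or that its reported incidence must be zero. The documents do not support that. What they support is that no CPK is scheduled, so planned data cannot give an incidence or a change from baseline.
- **The timing of the draws is consistent.** Visit text and schedule match, so how often to draw is a design choice in a 20-patient pilot. Telemedicine may also replace visits, and an added week 4 draw could force an attendance. This stands, and no added draw is proposed.
- **Bloods are not the only monitoring.** Tolerance is reviewed at weeks 4, 8 and 12, adverse events are assessed at every follow-up visit, and week 12 includes an examination with vital signs. This also stands: what is absent outside week 8 is bloods, not safety follow-up.

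**Conclusion.** The point holds as a gap in safety ascertainment of moderate weight. It does not touch the primary outcome.

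CPK, a laboratory effect that the protocol names, has 0 scheduled measurements. The chemistry lists differ by up to three analytes, including two from the liver panel. The one post-baseline sample is not clearly required to be new.

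A reader might go further and conclude that every patient completes dosing before any safety result is available. That follows only if treatment lasts 8 weeks. On the 12-week statement the week 8 result arrives during dosing, and the gap is instead the missing end-of-treatment sample. The documents do not settle which applies, so the firm conclusion is that the duration passages must be reconciled before the sample can be placed relative to dosing.

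The assessment assumes that the four laboratory descriptions are complete as published and that no separate laboratory manual adds CPK.

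**What to change.** 1. Add CPK to the screening and week 8 draws already in the schedule: 2 × 20 = 40 assays if all 20 patients complete both. If the sponsor prefers not to measure it, give the reason.
2. Make the screening and week 8 lists match the CMP definition in the schedule footnote, including bilirubin and alkaline phosphatase, and bring the Laboratory Tests item into line.
3. Replace the reused screening sentence in the week 8 entry with a statement that the results come from a new sample drawn for that visit.
4. Reconcile the 8-week and 12-week treatment passages, so that the sponsor can confirm where the single post-baseline safety sample falls relative to dosing.

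The cost is one analyte on existing draws, some wording and a protocol amendment. CPK may not be part of usual care, so it may have to be ordered as a research test. No extra draw, re-draw rule, treatment duration or action on an abnormal value is proposed; those are for the sponsor.
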